### 9.3.4. Catheter Type Pooling Analysis

Heterogeneity of outcomes by catheter type will be assessed for the primary endpoints by performing a logistic regression analysis with the primary endpoint outcome as the dependent variable and Catheter Type as the independent variable. Outcomes for the Blazer OI/IntellaNav OI catheters will be deemed to be heterogeneous with outcomes for the

IntellaTip MiFi OI/IntellaNav MiFi OI catheters if no statistical association is found between catheter type and the primary endpoint outcomes through the logistic models. A significance level of 15% will be used for this test.

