3.1.2 Sample size

The sample size estimate was obtained using the normal approximation to the binomial distribution and verified through simulations based on Kaplan-Meier methodology. The following assumptions were used in the sample size calculation:

Assumptions	Primary Safety
Expected rate	90% ²⁶
Performance goal	85%
Attrition (per year)	7.5%
Significance level (one-sided)	5%
Power	80%

Under the hypothesis and assumptions outlined above, the required sample size for this endpoint is 329 TREATMENT subjects.

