5.3 Center Pooling Analysis

Center-to-center heterogeneity will be assessed for the primary endpoints by performing a random effects logistic regression analysis. Centers with less than five enrollments will be combined to form “supercenters”. Small centers will be combined until the newly created supercenter has five enrollments, and then a new supercenter will be created. Centers will be deemed to be heterogeneous if the variance of the random center effect is found to significantly differ from zero. A significance level of 15% will be used for this test.

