5.4 Catheter Type Pooling Analysis

Heterogeneity of outcomes by catheter type will be assessed for the primary endpoints by performing a logistic regression analysis with the primary endpoint outcome as the dependent variable and Catheter Type as the independent variable. Outcomes for the Blazer OI/IntellaNav OI catheters will be deemed to be heterogeneous with outcomes for the IntellaTip MiFi OI/IntellaNav MiFi OI catheters if no statistical association is found between catheter type and the primary endpoint outcomes through the logistic models. A significance level of 15% will be used for this test.

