5.5 Additional Analyses

An analysis will be done for each primary endpoint stratifying results by catheter type (Blazer OI/IntellaNav OI and IntellaTip MiFi OI/IntellaNav MiFi OI).

Additional analyses will also be done to characterize the procedural workflow data in AF ablation cases with the Rhythmia Mapping System. Procedural workflow data will include, but not be limited to:

- electro-anatomical mapping information
- ablation gap detection (including gap detection techniques)
- ablation techniques (including use of DirectSense)

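### The catheter-family rule is inverted as written, and reversing it alone would leave a non-significant 15% test, with low power at the planned N, as the evidence that the two families have similar outcomes

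*SAP*

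**What the plan says.** SAP 5.4 describes the analysis as "performing a logistic regression analysis with the primary endpoint outcome as the dependent variable and Catheter Type as the independent variable". The two families are Blazer OI/IntellaNav OI and IntellaTip MiFi OI/IntellaNav MiFi OI. The verdict rule is that outcomes for the first family will be "deemed to be heterogeneous with outcomes for the IntellaTip MiFi OI/IntellaNav MiFi OI catheters if no statistical association is found". The condition in full is "if no statistical association is found between catheter type and the primary endpoint outcomes through the logistic models". The threshold is also given: "A significance level of 15% will be used for this test". Protocol 9.3.4 carries the same rule, including "IntellaTip MiFi OI/IntellaNav MiFi OI catheters if no statistical association is found between catheter type and the primary endpoint outcomes through the logistic models".

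The section just before it, SAP 5.3, runs the other way for centers: "Centers will be deemed to be heterogeneous if the variance of the random center effect is found to significantly differ from zero".

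SAP 5.5 adds: "An analysis will be done for each primary endpoint stratifying results by catheter type". It does not mention a between-family difference or an interval for one. Neither document gives a margin, a power figure or an expected split between families for the catheter-type test, and neither says what follows from the verdict.

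**The concern.** There are two problems, one behind the other.

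First, the direction is wrong. Finding no association is the result one expects when the families perform alike, yet the rule labels that result heterogeneous.

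Second, the obvious repair is to swap the direction so that an association means heterogeneous. A p-value of 0.15 or more would then become the plan's only formal ground for regarding the families as alike. Every sample size in the plan is for a single-arm test against a fixed goal, and none is for comparing two families. A non-significant result could easily coexist with a difference as large as the gap between the plan's expected safety rate and its performance goal.

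At stake is what the report may say about the MiFi catheters relative to the others. Protocol section 5 has this one study serve as the post-approval study for all four catheters, so readers will look to this analysis for that comparison.

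**Working it through.** **Inputs**

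- Test level 15% (SAP 5.4). Sidedness is not stated; two-sided is assumed, with critical value z = 1.440.
- N = 329: "the required sample size for this endpoint is 329 TREATMENT subjects" (SAP 3.1.2). Enrollment is 415 (Protocol 9.1.5). The latter is an upper bound for this analysis, because it includes INTENT and ATTEMPT subjects.
- Rates of 90% and 85% are the expected rate and goal for safety (SAP 3.1.2); 60% and 50% are those for effectiveness (SAP 3.2.2).
- The catheter split is not in the documents. A range from 50/50 to 90/10 is assumed.

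**The plan's own figure.** For 90% against 85%, one-sided 5% and 80% power, the exact one-sample binomial needs 304 subjects. Allowing for 7.5% attrition, 304/0.925 = 328.6, so 329. The plain normal approximation gives 283/0.925, so 306; with continuity correction it gives 302/0.925, so 327. The stated 329 is therefore reproduced, and it belongs to a single-arm test.

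**The rule as written.** With no true difference, a 15% test is non-significant about 85% of the time, so identical families are called heterogeneous about 85% of the time. With a true 90% versus 85% difference at 50/50, the same label is given about 52% of the time (next step). The label is less likely when the families differ.

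**The rule with the direction reversed.** Normal approximation at 50/50, 164.5 per family, 90% versus 85%:

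- SE under no difference = √(2 × 0.875 × 0.125 / 164.5) = 0.0365
- SE under the difference = √((0.09 + 0.1275) / 164.5) = 0.0364
- Power ≈ Φ((0.05 − 1.440 × 0.0365) / 0.0364) = Φ(−0.07) ≈ 47%

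Exact enumeration of two binomials with the logistic likelihood-ratio test gives 48%, a miss rate of 52%. Miss rates from the exact enumeration at N = 329:

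| Split | Safety 90% v 85% | Effectiveness 60% v 50% |
|---|---|---|
| 50/50 | 52% | 35% |
| 70/30 | 56–57% | 40% |
| 80/20 | 62–63% | 49% |
| 90/10 | 70–71% | 63% |

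Sensitivity at 50/50:

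- 415 analyzed: safety miss 45%, effectiveness miss 27%.
- 304 analyzed (after attrition), normal approximation: safety miss 55%.
- The 5 points placed at 95% v 90%, N = 329: miss 37–38%.

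For 80% power at 90% v 85% with equal families, the number per family is ((1.440 × √(2 × 0.875 × 0.125) + 0.842 × √0.2175) / 0.05)² ≈ 455, or about 910 in total.

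**What an interval would show.** Half-width of the 95% interval for the difference at 50/50 = 1.96 × √(p(1 − p)(1/165 + 1/164)). This is 6.5 points at p = 0.90 and 10.6 points at p = 0.60. Censoring is ignored, so real intervals would be somewhat wider.

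**The case against.** A reader might infer that the plan already treats non-significance as grounds for pooling. It does not: the literal text sends that result to heterogeneous. The absence-of-evidence criticism bites only once the direction is reversed. The center rule in SAP 5.3 suggests that reversal is what was meant, but the inversion is the defect actually on the page.

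A reader might also infer that a pooling decision, or study success, turns on this test. The documents do not support that. No action is tied to the verdict, success depends only on the two primary endpoints for the catheter family as a whole (SAP section 3 and 4.3), and SAP 5.5 reports each primary endpoint by family whatever the test shows. A visible difference would not be hidden.

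Nor is it safe to say that the test misses a 5-point safety difference at least half the time. That holds for 90% v 85% at N = 329, but not for 95% v 90%, nor for 415 subjects at 50/50. The 15% level, also used for subgroups and centers, fits a screen for signals, and as a screen it is reasonable.

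Finally, one might want a formal similarity margin. With a 5-point margin, an SE of 3.31 points and 90% in both families at 50/50, truly identical families would meet it only Φ(5/3.31 − 1.96) ≈ 33% of the time. The study was not sized for such a claim, and the gaps between expected rates and goals were set for another purpose.

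What remains is that the verdict rests on a p-value alone, in the wrong direction, and that the stratified results come without a stated between-family difference or interval.

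**Conclusion.** The point holds in limited form. The rule in SAP 5.4 and Protocol 9.3.4 is inverted. Correcting the direction alone would leave a rule that cannot support a statement of similar outcomes: at N = 329 the test misses a 90% v 85% safety difference in 52% of studies at an even split, and in 70–71% at 90/10. The figures assume a two-sided test, an unstated catheter split and no censoring. They improve with more analyzed subjects or a higher baseline rate. The effect is confined to what may be concluded about the two families; the primary tests and study success are untouched. It should be corrected, but it does not threaten the main result.

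**What to change.** In SAP 5.4 and Protocol 9.3.4:

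1. Reverse the rule, so that an association at the two-sided 15% level flags possible heterogeneity between the families.
2. For each primary endpoint, report the MiFi-minus-OI difference in 12-month Kaplan-Meier event-free rates with a two-sided 95% confidence interval, whatever the test result.
3. State that p ≥ 0.15 does not show that outcomes are similar.

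Do not add a mandatory similarity margin, and leave the pooled primary analysis as it is.

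The cost is a wording change in both documents and one extra estimate per endpoint, with no new data or subjects. The downside is that the intervals will be wide, as the half-widths above show, so the report will often be unable to say much about the families beyond the estimate and its uncertainty.

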5.5 Additional Analyses

An analysis will be done for each primary endpoint stratifying results by catheter type (Blazer OI/IntellaNav OI and IntellaTip MiFi OI/IntellaNav MiFi OI).

Additional analyses will also be done to characterize the procedural workflow data in AF ablation cases with the Rhythmia Mapping System. Procedural workflow data will include, but not be limited to:

- electro-anatomical mapping information
- ablation gap detection (including gap detection techniques)
- ablation techniques (including use of DirectSense)

5.6 Sensitivity Analyses

5.6.1 Sensitivity analysis for the primary safety endpoint analysis

The sensitivity analysis -- tipping point analyses will be performed in order to characterize the impact of missing data on the main primary safety endpoint outcome by determining the point at which events in these subjects could have impacted the primary safety endpoint outcome. For the primary safety tipping point analysis, the overall cohort will consist of all Treatment and Attempt subjects. Tipping point analyses will be performed using the exact binomial distribution.

Tipping Point Analysis – Only subjects with complete data (subjects experienced the primary safety endpoint event or patients followed through 12 months) will be considered to have full follow-up data. All subjects with missing data (Subjects who withdraw before 12 months without experiencing an endpoint event will be classified as having missing data) will one by one be considered to have experienced an endpoint event. The rate and one-sided Clopper-Pearson lower 95% confidence bound will be calculated and lower confidence bound compared to the performance goal of 85%. The number of missing data subjects who would have needed to experience an event for the endpoint to be failed will be considered the tipping point for this analysis.

5.6.2 Sensitivity analysis for the primary effectiveness endpoint analysis

The sensitivity analysis -- tipping point analyses will be performed in order to characterize the impact of missing data on the main primary effectiveness endpoint outcome by determining the point at which events in missing data subjects could have impacted the primary effectiveness outcome. For the primary effectiveness tipping point analysis, the overall cohort will consist of all Treatment subjects. The analysis will be performed using the exact binomial distribution.

Tipping Point Analysis- Only subjects with complete data (subjects experienced the primary effectiveness endpoint event or patients followed through 12 months) will be considered to have full follow-up data. Subjects with missing data (Subjects who withdraw or die before 12 months without experiencing an endpoint event will be classified as having missing data) will one by one be considered to have experienced an endpoint event. The rate and one-sided Clopper-Pearson lower 95% confidence bound will be calculated and lower confidence bound compared to the performance goal of

50%. The number of missing data subjects who would have needed to experience an event for the endpoint to be failed will be considered the tipping point for this analysis.

5.7 DIRECTSENSE subject related analysis

Additional analysis will be performed on data from all subjects where the DIRECTSENSE feature was used for their index procedure. Refer to the DIRECTSENSE Data Analysis Plan (WC# 92441955) for additional details.

6 CHANGES TO PLANNED ANALYSES

Any changes to the planned statistical analyses made prior to performing the analyses will be documented in an amended Statistical Analysis Plan approved prior to performing the analyses. Changes from the planned statistical methods after performing the analyses will be documented in the clinical study report along with a reason for the deviation.

7 PROGRAMMING CONSIDERATIONS

All statistical analyses will be conducted in SAS version 9.3 or higher (SAS Institute, Cary, N.C.)

